4.6.3 Methods for Reducing Bias

The following steps are being planned to mitigate/reduce bias towards the assessment of an NMO/NMOSD attack:

- 1 Study subjects will be instructed not to discuss AEs or NMO/NMOSD-related symptoms/medications with any of the independent assessors.
- 2 The EDSS rater will not have access to prior EDSS scores/FSS at the time of a new evaluation and will perform the evaluation of the subject without any knowledge of the subject's AE history or management of symptoms or findings from physical/neurological

examinations. The EDSS rater will be instructed NOT to elicit or discuss the subjects' experiences or AEs on the study. The EDSS rater must not manage the subject outside of the protocol for routine care or any other purpose. The EDSS scores will be captured electronically and transmitted to the investigator who will have access to the scores to compare against the protocol-defined criteria for an NMO/NMOSD attack. The EDSS scores/FSS will be monitored centrally by an independent expert.

- 3 The ophthalmology examiner will not have access to prior visual acuity and RAPD at the time of a new evaluation and perform the evaluation of the subject without any knowledge of the subject's AE history or management of symptoms or findings from physical/neurological examination. The ophthalmology examiner will be instructed NOT to elicit or discuss the subjects' experiences or AEs on the study. The ophthalmology examiner must not manage the subject outside of the protocol for routine care or any other purpose. The visual acuity scores and RAPD findings will be captured electronically and transmitted to the investigator who will have access to the score to compare against the protocol-defined criteria for an NMO/NMOSD attack.
- 4 The neuro-radiologist will not have access to the subject's AE history or management of symptoms or findings from physical/neurological examination.
- 5 To minimize the potential influence of MRI findings on clinical assessment of possible attacks, MRI images/study report should not be reviewed by the Principal Investigator unless a specific criterion for an attack requires review of the MRI. In such cases, review of the MRI image and local study report MUST be done AFTER all relevant clinical assessments are completed. The time sequence of all procedures and reviews required for assessment will be documented to demonstrate compliance.
- 6 To further minimize the potential influence of MRI findings on the adjudication of possible attacks, the AC will not be given access to the MRIs (where required) until after their evaluation of the clinical data is complete.
- 7 To minimize the potential influence of the Principal Investigator's review on the AC, the AC will not be provided with the Principal Investigator's opinion as to whether an attack has occurred or not, nor will the AC receive information about which protocol attack criterion was met and the rescue medication utilized.
- 8 To assess for a potential bias in the investigator's assessment of new symptoms, the data generated from this assessment, which determined that the symptoms were not related to NMO/NMOSD, will be sent to review by the AC. The level of agreement between the investigator and the AC will be assessed.

4.6.4 Methods for Unmasking

The treatment code should not be broken except in medical emergencies when the appropriate management of the subject requires knowledge of the treatment randomization. The

investigator documents and reports the action to MedImmune, without revealing the treatment given to subject to the MedImmune staff.

MedImmune retains the right to break the code for SAEs that are unexpected and are suspected to be causally related to an investigational product and that potentially require expedited reporting to regulatory authorities.

4.6.4.1 Unmasking in the Event of a Medical Emergency

In the event of a medical emergency, the investigator must first attempt to contact the medical monitor to discuss the medical emergency and the reason for wanting to unmask the subject's investigational product allocation prior to proceeding with unmasking. (Czech Republic only: in the event of a medical emergency that may be related to investigational product, the investigator may unmask an individual subject's investigational product allocation if he/she feels it is required without prior contact to the medical monitor/sponsor.) Unmasking should occur only if the subject's medical emergency would be managed differently as a result of the subject's having received investigational product. In most cases, management of the medical emergency would be the same whether or not the subject received investigational product. If this is the case, the investigational product allocation should *not* be unmasked.

In exceptional circumstances, where in the clinical judgment of the investigator the medical emergency necessitates that the subject's investigational product allocation be immediately unmasked, the investigator may proceed with unmasking without prior discussion with the medical monitor.

Instructions for unmasking an individual subject's investigational product allocation are contained in the IVRS/IWRS manual.

4.6.4.2 Unmasking for Interim Analysis Purposes

An unmasked interim analysis is planned for this study as described in Section 4.8.10. The interim analysis to determine futility will be conducted by the DMC; Sponsor, and sites will remain masked to the treatment assignment post-interim analysis.

4.6.4.3 Unmasking due to Known or Hypothesized Effects of MEDI-551

MEDI-551 is known to deplete CD19+ B-cells; therefore, the results of flow cytometry to count B-cells are potentially unmasking. These data will not be made available to investigation sites post randomization through the remainder of the study.

Data from early phase development in non-oncology subject populations receiving MEDI-551 suggest that MEDI-551 administration may be associated with potential unspecified mild reduction in total Ig in individual subjects. Since this reduction may be potentially unmasking, these data will not be made available to investigational sites post randomization through the remainder of the study.

MEDI-551 is hypothesized to reduce titers of AQP4-IgG. AQP4-IgG titers from the central laboratory will not be made available to investigational sites at any point in the study.

MEDI-551 is known to reduce the plasma cell gene signature. Because the results of the plasma cell gene signature assay could potentially be unmasking, these samples will not be tested prior to un-masking of the study.

MEDI-551 may also reduce tetanus vaccine titers; therefore, the results of the vaccine titer assay will not be made available to the sites at any point during the study.

Any potentially unmasking data from the protocol will not be available to the sponsor until the study has been unmasked following completion of the RCP.

Investigators must not request any potentially unmasking laboratory results at a local or other central laboratory.

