If a subject withdraws during a scheduled study visit, that visit will change to an EDV and procedures should be conducted according to those presented for Day 365/EDV for the OLP.

At the point the Sponsor decides to terminate the OLP, the next visit for all ongoing subjects in that period will be an EDV to capture all assessments; this would also represent the first visit of the SFP.

Table 7 Schedule of Open-label Period Study Procedures

Study Period	Open-label Period										
	0	2	4	13	26	39, then Q26W	52, then Q26W/EDV				
Week											
Day	1	15	29	92	183	274+	365+				
Visit Window	(+ 14d from Day 197 RCP or +28d AC Determination)	± 3d	± 3d	± 14d	± 7d	± 14d	± 7d				
Procedure/Visit Number	1	2	3	4	5	6, 8,10, etc	7, 9, 11, etc				
Written informed consent	X										
SF-36v2 Health Survey				X	X	X	X				
Pain NRS			X	X	X	X	X				
Modified Rankin Scale			X	X	X	X	X				
Physical/neurological examination	X ^a	X	X	X	X	X	X				
C-SSRS (“Since Last Visit” version) ^h	X ^a	X	X	X	X	X	X				
Vital signs	X ^a	X	X	X	X	X	X				
Collect blood for:											
Hematology and serum chemistry	X ^a	X	X	X	X	X	X				
MEDI-551 ADA	X ^a			X	X	X	X				
Total Ig, IgM, IgG, IgA, IgE	X ^a			X	X	X	X				
Whole blood for flow cytometry (B-cell count and cell subsets)		X	X	X	X	X	X				
Serum for AQP4-IgG assay (titers)	X ^a		X	X	X		X				
Whole blood for gene expression			X	X	X		X				
Serum for exploratory biomarkers		X	X	X	X	X	X				
Vaccination titers (tetanus) ^j				X	X		X				

Table 7 Schedule of Open-label Period Study Procedures

Study Period	Open-label Period										
	0	2	4	13	26	39, then Q26W	52, then Q26W/EDV				
Week											
Day	1	15	29	92	183	274+	365+				
Visit Window	(+ 14d from Day 197 RCP or +28d AC Determination)	± 3d	± 3d	± 14d	± 7d	± 14d	± 7d				
Procedure/Visit Number	1	2	3	4	5	6, 8,10, etc	7, 9, 11, etc				
Collect urine for:											
Urine HCG (females with childbearing potential only; pre-IV dose only)	X ^b	X			X		X				
Urinalysis	X ^a	X	X	X	X	X	X				
Assess subject for new/worsening symptoms related to NMO/NMOSD ^c	X ^b	X	X	X	X	X	X				
Independent EDSS/FSS administration ^h	-			X	X	X	X				
Independent ophthalmology examination (high-/low-contrast visual acuity test, RAPD assessment)				X	X	X	X				
Neuroaxis MRI (including optic nerve)	(X) ^d						X ^e				
Investigational product administration	X ^b	X ⁱ			X		X ^g				
Assessment of AEs/SAEs (including infusion reactions)	X ^b	X	X	X	X	X	X				
Concomitant medications	X ^b	X	X	X	X	X	X				

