- Human immunodeficiency virus (HIV)-1,-2 antibody (screening only)
- Polyomavirus JCV antibody titers (serum to be collected at screening only and frozen for future testing, if required).
- In a case of suspected PML, a CSF sample for JCV DNA polymerase chain reaction (PCR) will be collected and frozen immediately.
- Tetanus vaccination titers
- Total Ig, IgM, IgG, IgA, IgE

Other Tests

- Serum autoantibodies

Estimated Glomerular Filtration Rate

The estimated GFR must be ≥ 60 mL/minute for study eligibility to minimize the risk of developing nephrogenic systemic fibrosis upon receiving Gd-containing contrast agents. The estimated GFR will be calculated by the central laboratory based on the plasma and urine creatinine samples provided using the Modification of Diet in Renal Disease formula. Glomerular filtration rate eligibility must be confirmed by the site on receipt of the central laboratory report and prior to randomization.

Vaccination Titers

Serum samples for anti-tetanus vaccine antibody titers will be collected from all subjects according to the schedules of procedures in Table 6 and Table 7. The assay will be conducted by the central laboratory and further details will be provided in the Laboratory Manual.

Because MEDI-551 may reduce vaccine titers, the levels reported for this study by the central laboratory will not be made available to the sites or to the sponsor at any point during the study prior to unmasking of the study.

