4.3.9 Biomarker Evaluations and Methods

Samples for measurement of biomarkers listed below will be collected according to the schedules of procedures in Table 6, Table 7, and Table 8. Detailed procedures for sample collection, processing, storage, and shipment are presented in the Laboratory Manual provided to the study site

Serum for AQP4-IgG Serostatus Assay

The AQP4-IgG serostatus assay will be used to determine AQP4-IgG serostatus for stratification purposes. The assay will be conducted by a central laboratory using a commercially available visual fluorescence-observation cell binding assay (EUROIMMUN) that has been validated to Clinical Laboratory Improvement Amendment/College of American Pathologists standards. The method involves detection of IgG binding to cells expressing recombinant AQP4. The serostatus of each subject will be provided to the site prior to randomization.

The screening, baseline, and study visit assays used to determine AQP4-IgG titer will be conducted by a central laboratory using a quantitative flow cytometry assay based on binding of IgG to cells transfected with AQP4. Serum will be collected for the measurement of serum

AQP4-IgG by flow cytometry at visits specified in Table 5, Table 6, Table 7, Table 8, and Table 9.

Because MEDI-551 is hypothesized to reduce AQP4-IgG titers the AQP4-IgG titer levels reported for this study by the central laboratory will not be made available to the sites or the sponsor at any point during the study prior to unmasking of the study.

Whole Blood for Flow Cytometry

Whole blood samples for quantification of relevant immune cells will be collected according to the schedules of procedures in Table 5, Table 6, Table 7, Table 8, Table 9, and Table 10. Flow cytometry performed at a central laboratory will be used to enumerate B-cell, T-cell, and natural killer (NK)-cell levels and to conduct immunophenotyping analyses of various B-cell subsets.

MEDI-551 is known to deplete CD19+ B cells. Therefore, in this study, the results of flow cytometry for B-cell counts could potentially be unmasking. For this reason, these data will not be made available to the sites or the sponsor from post-randomization through the remainder of the study prior to unmasking of the study.

Whole Blood for Gene Expression

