6.3 Study Timetable and End of Study

The end of the study ("study completion") is defined as the date of the last protocol-specified visit/assessment (including telephone contact) for the last subject in the study. This will occur when the last subject completes the 52-week SFP.

An individual subject will be considered to have completed the RCP if the subject was followed through Day 197 or experienced an NMO/NMOSD attack as determined by the AC, regardless of the number of doses the subject received. Additionally, all subjects enrolled in the RCP at time that the 67th AC-determined attack is confirmed, or at the time the Sponsor discontinues enrollment upon recommendation of the independent DMC based on evidence of efficacy and safety, will also be considered as completers, regardless of the number of doses the subject received, provided the subject completes the Day 197/EDV visit. A subject will be considered to have completed the OLP if the subject participated for the duration of the OLP as per Section 3.1.1.4. A subject will be considered to have completed the SFP if the subject was followed for 52 weeks (12 months) after the last dose of investigational product. Subjects will be considered not to have completed a study period if consent was withdrawn, death occurred, or the subject was lost to follow up.

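### The bar on sites seeing total Ig results (Protocol 4.6.4.3) has no end at RCP unmasking, so read literally it runs through the OLP and SFP

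*Protocol*

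**What the plan says.** Protocol 4.6.4.3 lists the laboratory results that could reveal treatment. For total Ig it gives one reason, that a reduction might be unmasking, and then states that "these data will not be made available to investigational sites post randomization through the remainder of the study". The B-cell sentence in the same section is almost identical: "These data will not be made available to investigation sites post randomization through the remainder of the study". Neither sentence ends the bar at unmasking.

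The only sentence in 4.6.4.3 that ties access to the end of the RCP concerns the sponsor. Potentially unmasking data "will not be available to the sponsor until the study has been unmasked following completion of the RCP". The section closes with a ban on outside testing: "Investigators must not request any potentially unmasking laboratory results at a local or other central laboratory".

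Section 6.3 defines when the study is over: "This will occur when the last subject completes the 52-week SFP".

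Section 4.3.6 lists total Ig and its classes among the other safety tests and gives no access rule for them. Tables 7, 8 and 10 schedule Ig in the OLP, at Assessment Visits and in the SFP.

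**The concern.** Withholding Ig from sites while the RCP is running is right and is not questioned here. The difficulty is that the restriction outlasts most of its reason. Once RCP data are closed and unmasked, every OLP subject is known to be on MEDI-551. The sponsor may then see Ig values, while the physician deciding on the next infusion of a B-cell-depleting antibody may not.

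The protocol treats Ig as relevant to safety. Total Ig below 600 mg/dL is an exclusion under infection risk (4.1.3, criterion 23a). Ig is one of the few things followed in the SFP (3.1.1.5). SAP 3.7.1.1 lists infections and opportunistic infection as events of special interest.

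Section 5.1 makes an abnormal laboratory finding an adverse event when the investigator judges it medically significant. A site cannot make that judgment on a value it has not been shown. In the SFP no medication is prohibited (4.7.2), so a site could start another immunosuppressant without the scheduled Ig results.

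**Working it through.** No calculation applies. The check is a comparison of every access rule in the current protocol text and the SAP, leaving the amendment log aside.

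**1. How long the bar runs.** It starts at randomization and lasts for the rest of the study. By 6.3 that is the last subject's final SFP visit, so the OLP and SFP are included.

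**2. Whether another section ends it.**

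| Result | Rule in 4.6.4.3 | Rule elsewhere | End stated for sites |
|---|---|---|---|
| Total Ig | Barred to sites | None found | None |
| B-cell counts | Barred to sites | 4.3.9: barred to sites and sponsor "through the remainder of the study prior to unmasking of the study" | Unmasking, in 4.3.9 only |
| AQP4-IgG titers | Barred to sites | 4.3.9: barred before unmasking | Unmasking, in 4.3.9 only |
| Tetanus titers | Barred to sites | 4.3.6: barred to sites or "to the sponsor at any point during the study prior to unmasking of the study" | Unmasking, in 4.3.6 only |
| Plasma cell gene signature | Not assayed before unmasking | 4.3.9: same | Unmasking |

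For the sponsor, 4.6.4.3 ends the bar on all such data at unmasking after the RCP. Ig is therefore the only result in the table with no stated end for sites anywhere. The SAP analyses Ig but has no rule on release to sites.

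**3. Whether the reason lasts as long as the bar.** The primary and the four key secondary endpoints use RCP data, so Ig values released after RCP unmasking cannot affect them. Two things remain. Section 4.6.2 masks the OLP Day 15 infusion so that sites do not learn the RCP arm, and gives no end date. Sites also decide which OLP symptoms go forward as possible attacks (4.3.1.1). Most of the reason has gone, but not all of it.

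**4. What sites would see meanwhile.** Table 7 draws Ig on OLP Day 1 (unless the last RCP draw serves) and at weeks 13, 26, 39 and 52. The last two visits then each repeat every 26 weeks, so draws fall about every 13 weeks, with dosing every 26 weeks. The chemistry panel at those visits includes total protein and albumin (4.3.6), an indirect guide. Table 10 draws Ig every 3 months in the SFP and has no chemistry panel, so that guide is missing there.

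**The case against.** The case for leaving the text alone has several good parts.

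- The B-cell sentence is only a mismatch with 4.3.9, which already ends that bar. This stands: for B cells the matter is consistency of wording and nothing more.
- No passage says that sites learn the RCP arm when the sponsor does, so longer masking of sites is consistent with 4.6.2. This stands as a trade-off, but it weakens once RCP data are closed and all subjects are on MEDI-551.
- The expected Ig effect is described as mild, no discontinuation rule in 4.1.6 uses Ig, and Protocol 5.3 names only Hy's law cases and PML as events of special interest. All true. No specified dosing decision would change.
- Safeguards exist: DMC safety review (4.8.8), sponsor access after unmasking, the sponsor's power to stop dosing for an adverse event (4.1.6), annual safety updates (SAP Table 3.1-1), and no infusion during a clinically significant infection (4.5.1.2). These are real but partial. None puts the individual Ig value before the treating physician.
- A duty to release results goes further than 4.3.9, which ends a bar without promising release. This is fair, so release has to be proposed in its own right.

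A reader might infer that sites can obtain no Ig value at all after unmasking. The documents do not support that. The testing ban covers only results that could unmask, so it arguably lapses by its own terms, although the text does not say so.

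**Conclusion.** The point holds for Ig. Section 4.6.4.3 is the only access rule for a listed safety test. Read literally, it keeps scheduled results from sites to the end of the SFP, while the sponsor's bar ends at RCP unmasking. This is a cheap improvement and does not threaten the trial's conclusions.

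Two stronger readings should be resisted. One is that subjects are harmed: nothing in the documents shows this. The other is that a definite number of results per subject is lost. Any count needs an assumed lag to unmasking and an assumed OLP length. The plan gives no unmasking date, and regulatory approval, end of development or early exit can shorten the OLP, so few or no OLP draws might be affected. I give no bound.

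The verdict rests on the literal wording of 4.6.4.3 and 6.3. A few pages are missing from the available copy, and the separate Laboratory Manual could not be checked. If the sponsor already intends release after unmasking, the protocol should say so.

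**What to change.** In 4.6.4.3, limit the Ig restriction on sites and the ban on local testing to the period before the study is unmasked, as 4.3.9 and 4.3.6 do for other results. State that OLP and SFP Ig results go to sites once the RCP has been unmasked. Keep the Adjudication Committee blinded to them. Section 4.3.1.5 names B-cell counts and AQP4-IgG titers as examples of what the committee must not see, and Ig should be added. Align the B-cell sentence with 4.3.9 for consistency only. No dosing rule is needed; use of the values stays with clinical judgment.

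The cost is a wording change and a switch in central-laboratory reporting. There are two downsides. Sites might infer the RCP arm after RCP data are closed. Ig values might also slightly influence which OLP symptoms are referred, a step that blinding the committee does not protect. The second would affect only the annualized attack rate, which is summarized descriptively (Protocol 4.8.3.3, SAP 3.4.2.3).

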4.7 Restrictions During the Study and Concomitant Treatment(s)

The investigator must be informed as soon as possible about any medication taken from the time of screening until the end of the study (final study visit). Any concomitant medication(s), including herbal preparations, taken during the study will be recorded.

4.7.1 Permitted Concomitant Medications

Investigators may prescribe concomitant medications or treatments deemed necessary to provide adequate supportive care except for those medications identified as “excluded” as listed in Section 4.7.2. Specifically, subjects should receive full supportive care during the study, including transfusions of blood and blood products, and treatment with antibiotics, anti-emetics, anti-diarrheals, and analgesics, and other care as deemed appropriate, and in accordance with their institutional guidelines.

Subjects who experience an NMO/NMOSD attack should be given rescue therapy according to the judgment of the investigator as described in Section 4.5.2.2.

All concomitant and rescue therapy given to the subject during the study will be recorded on the source document and includes, but is not limited to, the dose, start and stop dates, frequency, route of administration, and reason for administration.

